2004). In addition, the regular supervised prescription regimen may by itself help the patient to structure his daily life. Oral application of sustained release dexamphetamine, with a much slower onset and limited peak effect than crack-cocaine, clearly meets the rationale for substitution treatment. As in any medication study, the primary focus of our study will be on the balance between (potential) benefit and harm produced by the medication, taking into consideration the personal and societal damage associated with continued illicit use of cocaine, in a situation without effective pharmacological treatment options.

STUDY OBJECTIVE

The overall objective of this feasibility study is to investigate the usefulness of sustained release dexamphetamine in the treatment of cocaine dependence, and – dependent upon the results of both this study and the parallel studies of topiramate and modafinil (see Preface) – to yield one or more candidate medications for future investigation in a large-scale confirmatory controlled trial. Specifically, the study aims to evaluate, in crack dependent patients with comorbid heroin dependence, the response to medically prescribed oral dexamphetamine SR (60 mg/day) as an add-on to heroin-assisted treatment, in terms of potential efficacy, acceptance, compliance, safety, and patient satisfaction.

GENERAL STUDY DESIGN

The study will be conducted using a multicenter, double-blind, placebo-controlled, randomized treatment design. Following screening and baseline assessment, eligible patients in a heroin-assisted maintenance treatment program will be randomly allocated (ratio: 1:1) by the collaborating pharmacist to (continued) heroin-assisted treatment plus 12 weeks treatment with placebo (control group; n=36) or to (continued) heroin-assisted treatment plus 12 weeks treatment with sustained release dexamphetamine 60 mg/day (experimental group; n=36). Randomization will be concealed, using a computer-generated randomization list, and will be prestratified by treatment center (4 treatment centers). Study assessments will take place at baseline, and 4, 8, and 12 weeks after baseline. The primary time point at which treatment outcome will be determined is 12 weeks after baseline.

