Control treatment consists of ongoing heroin-assisted treatment (as described above) plus 12 weeks treatment with placebo. Placebo (2 tablets/day) will be matched to sustained release dexamphetamine tablets, and will be dispensed once daily during the patient’s morning visit at the treatment center. For the purpose of the present study, the placebo tablets were manufactured by the Slotervaart pharmacist (group of [name]), in compliance with the principles and guidelines of good manufacturing practice (see appendix: IMP-dossier, July 2013).

Experimental treatment consists of ongoing heroin-assisted treatment (as described above) plus 12 weeks treatment with sustained release dexamphetamine sulfate, prescribed in a fixed, single oral dose of 60 mg/day (2 tablets of 30 mg each). Oral sustained release dexamphetamine dose-levels of 30-60 up to 110 mg/day have been used in several studies in methamphetamine (Galloway et al., 2011; Longo et al. 2010) and cocaine dependent (Grabowski et al., 2001, 2004b) patients. In addition, oral dexamphetamine is prescribed to amphetamine users with heavy, problematic use in the United Kingdom at doses ranging from 5-200 mg/day (Bradbeer et al., 1998). Sustained release dexamphetamine has an average elimination half-life of approx. 12 hours, will be dispensed once daily during the patient’s morning visit at the treatment centre, and – to allow intensive safety monitoring – must be taken under supervision at the treatment site. In addition, weekly assessments of heart rate and blood pressure will be conducted during the entire study period of 12 weeks. For the purpose of the present study, sustained release dexamphetamine sulfate tablets of 30 mg each were manufactured by the Slotervaart pharmacist (group of [name]), in compliance with the principles and guidelines of good manufacturing practice (see appendix: IMP-dossier, July 2013).

In case a patient terminates his/her study treatment before week 12, or is withdrawn from the study for medical reasons, he/she will not be replaced by another patient. Following the end of the 12 weeks trial period, patients will continue their heroin-assisted treatment, but the study medication (either placebo or sustained release dexamphetamine; due to blinding unknown to both the treatment physician and research staff) will be terminated in all patients, and all usual treatment options in Dutch addiction care will be available to the patients, if indicated.

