The study data will be analyzed following an intent-to-treat (ITT) approach. The ITT-population consists of all randomized patients who received at least one dose of the prescribed medication. The end of the trial is defined as the last visit of the last patient undergoing the trial. Effect of the intervention will be evaluated in terms of potential efficacy – cocaine use (self-report; urinalyses) and craving for cocaine, use of other substances, physical and mental health, social functioning (including criminality) – as well as in terms of acceptance, medication compliance, safety, and patient satisfaction.

The primary outcome measure pertains to cocaine use, defined as the total number of days of crack-cocaine use during the 12 weeks study period (range: 0 – 84 days), and will be analyzed in a multivariate regression analysis, controlling for study group and treatment site interactions. Secondary effects of the interventions will be evaluated in terms of additional cocaine use related outcome measures (e.g., longest duration of cocaine abstinence, and the number of days cocaine abstinence as well as the mean proportion of cocaine metabolite-free urine samples in the four weeks preceding the week 12 assessment), cocaine craving, use of other substances (self-report), physical and mental health, social functioning (including criminality), and patient satisfaction. Depending on the measurement level of the secondary outcome measure, differences between the two study groups will be analyzed using 2 (time) x 2 (group) repeated measures ANOVA, multivariate (logistic) regression analyses, and GEE-modelling.

Concerning missing data, multiple imputation will be applied for missing interview data. Missing urine samples (two samples/week in weeks 9 to 12) will be considered cocaine-positive.

Since the medication will be dispensed on a daily basis and medication intake will be supervised, compliance with the study medication can be registered reliably on a daily basis. Differences between the study groups (dexamphetamine *versus* placebo) will be described and analyzed in terms of the total number of days in which the medication was taken during the 12 weeks study period, the number of consecutive weeks in which patients were fully compliant (i.e., daily medication intake), and medication intake in the four weeks preceding the week 12 assessment.

Emergency unblinding

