In the primary analysis, treatment effect will be investigated by means of a multivariate regression model with the total number of days of crack-cocaine use during the 12 weeks (84 days) study period as primary outcome measure (see above). The difference between the sustained release dexamphetamine and placebo study groups in total number of days of crack-cocaine use during 12 weeks treatment, is estimated to be 10 days, with a pooled standard deviation of 17 days (i.e., moderate effect size). Given the feasibility character of the study, the sample size should preferably be limited. As in the parallel studies of topiramate and modafinil ("New pharmacotherapeutic treatment options for crack-cocaine dependent people in the Netherlands"; NL22193.018.09; MEC09/197) we, therefore, have chosen for a lenient alpha of 0.10 to minimize loss of statistical power due to small sample size, instead of the usual 5% false-positive rate, which would be more appropriate for a future confirmatory trial. Given the two-sided alpha=0.10, and a 1-beta power of 0.80, n=36 patients are required in each study group (2x36=72 patients for the present study) (Pocock, 1983; Cohen, 1988).

SAFETY MONITORING AND REPORTING

Adverse events and adverse reactions

Adverse events (AEs) are defined as any undesirable medical experience occurring to a study subject during the study. All AEs reported spontaneously by the subject or observed by the treating physician or his staff will be registered on a weekly basis by the treating physician, defining the relationship of each AE with the study medication (definitely not, possibly, probably, certainly, unknown), and its severity. The severity of AEs will be recorded as follows:

- mild: the AE is transient and easily tolerated;
- moderate: the AE causes the subject discomfort and interrupts the subject's usual activities;
- severe: the AE causes considerable interference with the subject's usual activities and may be incapacitating or life-threatening.

All AEs will be followed until they have abated, or until a stable situation has been reached.

Adverse reactions (ARs) are defined as all undesirable responses to the study medication related to any dose administered.

Unexpected adverse reactions are adverse reactions, of which the nature or severity is not consistent with the side effects (adverse reactions) of sustained release dexamphetamine sulfate described above.

Serious adverse events and unexpected serious adverse reactions

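### The set called ITT excludes randomised patients who never take a dose, so compliance in each arm can be overstated, though the between-arm comparison is largely protected

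*Protocol*

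**What the plan says.** The section Outcome Measures and Data Analysis opens with a general rule: "The study data will be analyzed following an intent-to-treat (ITT) approach". It then defines the population: "The ITT-population consists of all randomized patients who received at least one dose of the prescribed medication". The protocol defines no second analysis set and makes no exception for any outcome.

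The Study Objective is to evaluate the response to dexamphetamine SR "in terms of potential efficacy, acceptance, compliance, safety, and patient satisfaction". The analysis section repeats that the intervention will be judged on efficacy "as well as in terms of acceptance, medication compliance, safety, and patient satisfaction".

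Compliance has three stated measures, each compared between arms: "the total number of days in which the medication was taken during the 12 weeks study period", the number of consecutive weeks with daily intake, and intake in the four weeks before the week 12 assessment. Because dispensing is daily and intake is supervised, the protocol says that "compliance with the study medication can be registered reliably on a daily basis". Acceptance is named but given no measure.

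Under Study Treatments, a patient who stops early or is withdrawn for medical reasons stays unreplaced: "he/she will not be replaced by another patient". Nothing provides for a patient who is randomised and never starts.

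**The concern.** Membership of the set depends on an event after randomisation, namely taking the first tablet. For compliance that event is part of the outcome. A patient who takes one tablet and stops counts as 1 day of 84. A patient who takes none, and whose value of 0 is known rather than missing, is not counted at all. A study meant to learn how well patients take the drug has no reason to draw the line there.

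At stake is the descriptive level of compliance in each arm. Planners of a later confirmatory trial would read that level as applying to patients randomised, when it applies only to patients who started. The label adds to the risk, because a reader who sees ITT in a report will assume that everyone randomised is in the denominator.

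**Working it through.** **The plan's own figure.** Power Considerations states that the difference "is estimated to be 10 days, with a pooled standard deviation of 17 days", with two-sided alpha 0.10 and power 0.80. By the normal approximation, n per arm = 2 × [17 × (1.645 + 0.842) / 10]² = 35.7, rounded up to 36. This matches the protocol, and the power at 36 per arm is 0.803. The sample size is not in dispute; 36 serves below as the denominator.

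**Can a never-dosed patient arise?** Consent comes before baseline screening (Ethical Considerations). Randomisation follows screening and baseline assessment (General Study Design). The first tablet is taken under supervision at a morning visit (Study Treatments), and patients may leave at any time. The case is therefore possible. The provision that keeps patients in the ITT analysis after emergency unblinding concerns patients whose study treatment is then stopped, and does not bring in those who never began.

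**Effect on mean days taken.** Let m be the mean days among dosed patients and u the number never dosed out of 36 in an arm. Never-dosed patients contribute 0 days.

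- All-randomised mean = m × (36 − u) / 36
- Overstatement by the dosed-only set = m × u / 36

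The protocol gives neither m nor u. The ranges below are assumptions.

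| Dosed mean m | u = 0 | u = 1 | u = 2 | u = 4 |
|---|---|---|---|---|
| 60 | 0 | 1.7 | 3.3 | 6.7 |
| 70 | 0 | 1.9 | 3.9 | 7.8 |
| 80 | 0 | 2.2 | 4.4 | 8.9 |

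(Entries are days of overstatement out of 84.) At m = 70 the all-randomised mean is 68.1, 66.1 or 62.2 days for u = 1, 2 or 4, where the plan would report 70. In relative terms the reported mean drops by u/36, which is 2.8%, 5.6% or 11.1%. The direction does not depend on the assumptions, since adding zeros cannot raise a mean.

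**Effect on the primary outcome.** If all randomised patients are analysed and an undosed active-arm patient has no drug effect, the assumed 10-day difference becomes 10 × (36 − u) / 36: 9.7 days for u = 1 and 8.9 days for u = 4. If u patients per arm are excluded instead, the set shrinks and power (normal approximation) falls from 0.803 to 0.793 for u = 1 and to 0.761 for u = 4.

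**The case against.** The strongest reply is that the event may hardly occur. Participants already attend the same centres for supervised heroin-assisted treatment, available up to three times a day, seven days a week. The tablets are given at the usual morning visit. Willingness to take part in the study treatment is an inclusion criterion, and patients have about two weeks to consider consent. The number never dosed could be zero, and then the two sets coincide. This stands, and it is why the assumed range starts at 0.

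Some stronger readings are tempting but not supported by the document:

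- *The treatment comparison is biased.* The tablets are matched and the trial is double-blind, so refusal before the first dose should not depend on the arm. This largely protects the comparisons between arms, including the one on cocaine use.
- *Acceptance is bound to come out at 100%.* That presumes acceptance means starting treatment. The protocol gives acceptance no measure, and a statistical analysis plan may do so. The effect can be shown exactly only for compliance; for acceptance it is conditional.
- *The choice of candidate drug will be distorted.* The Study Objective makes that choice depend on this trial and the parallel ones, but sets no threshold for compliance or acceptance. No decision rule is shown to change.
- *Every never-dosed patient has refused the drug.* Other reasons are possible. A score of 0 days is right for compliance whatever the reason, but reasons should be recorded before any such patient is called a non-accepter.

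It can also be said that the definition stands right beside the label, so an attentive reader is not misled, and that daily records keep never-dosed patients identifiable. Both are true. Neither puts those patients back into the compliance analysis as the protocol states it.

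**Conclusion.** The point holds in a limited form. The protocol fixes a modified ITT set under the name ITT, applies it to all study data, and so leaves out of the compliance outcome randomised patients whose value is known to be 0. The compliance level reported in each arm is equal to or higher than the all-randomised level; any measure of acceptance based on starting treatment would behave the same way.

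The size is 0 to 8.9 days of 84, assuming 0 to 4 never-dosed patients of 36 per arm and dosed means of 60 to 80 days. One never-dosed patient at a mean of 70 gives 1.9 days. The protocol supplies none of these inputs except the 36 and the 84, and the true number never dosed may be zero. This is a low-cost correction to a stated rule. It does not threaten the treatment comparison or the sample size.

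**What to change.** 1. Analyse compliance, and any measure of acceptance based on starting treatment, in all randomised patients by allocated arm. Score never-dosed patients as 0 days taken and 0 fully compliant weeks.
2. Report the number of never-dosed patients in each arm, with reasons.
3. Rename the set that requires a dose modified ITT.
4. If that set is kept for the primary outcome, give the all-randomised result as a sensitivity analysis.

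For compliance this changes only wording: the randomisation list and the daily dispensing records per patient (Drug accountability) already hold the data. The downside is a slightly less favourable compliance figure. The all-randomised sensitivity analysis would also show a slightly diluted effect on cocaine use, about 9.7 instead of 10 days if one active-arm patient is never dosed.

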At baseline, the following self-report instruments will be administered: the Composite International Diagnostic Interview Substance Abuse Module (CIDI-SAM; cocaine and alcohol dependence; Cottler, 2000), as well as questions on suicidal risk from the MINI International Neuropsychiatric Interview (MINI; Sheehan et al., 1998); the short version of the Addiction Severity Index (ASI; McLellan et al., 1980, 1992; Hendriks et al., 1989), supplemented with questions about current illegal activities, income, and living arrangements (similar to the ASI-version used in the CRF of the Dutch RCT on medically prescribed heroin); the Time Line Follow-Back (TLFB, pertaining to cocaine use in the previous month; Sobell & Sobell, 1992); the Maudsley Addiction Profile-Health Symptoms Scale (MAP-HSS; Marsden et al., 1998); the Symptoms Check List-90 (SCL-90; Derogatis et al., 1993; Arrindel & Ettema, 1996); the Obsessive Compulsive Drug use Scale (OCDS; Anton et al., 1996; De Wildt et al., 2005), the EuroQol (EQ-5D; Brooks, 1996), and the Readiness to Change Questionnaire (RCQ; Defuentes-Merillas et al., 2002).

At the 12 weeks assessment, (follow-up versions of) each of these instruments will be administered again, with the exception of the CIDI, MINI and RCQ. In addition, patient satisfaction (Client Satisfaction Questionnaire; CSQ-8; De Wilde & Hendriks, 2005), supplemented with questions pertaining to the received medication (placebo or sustained release dexamphetamine) will be assessed.

At the 4 and 8 weeks assessment, the TLFB (pertaining to cocaine use in the previous month) and the ASI-items pertaining to other substance use will be administered, as well as the MAP-HSS, SCL-90, OCDS, and EQ-5D.

Additional assessments include blood sampling (laboratory screen: BSE, MCH, MCV, MCHC, GGT, ALAT, ASAT, alkalase phosphate, leucocytes, thrombocytes) (screening/baseline assessment and 12 weeks assessment; 2 x 16 ml), ECG (screening/baseline assessment and 12 weeks assessment), weekly medical screening; weekly check on heart rate and blood pressure during the entire study period; two times/week urine sampling (cocaine metabolites) during the 4 weeks preceding the 12 weeks assessment; monthly pregnancy testing (females); weekly registration of adverse events, serious adverse events (see: Safety reporting), and co-medication; study drug accountability (placebo and sustained release dexamphetamine); treatment compliance.

OUTCOME MEASURES AND DATA ANALYSIS

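### The primary regression as written names no baseline days of cocaine use as a covariate: an unused gain in precision, not a shortfall in power

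*Protocol*

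**What the plan says.** The section on outcome measures and data analysis defines the primary outcome as the count of crack-cocaine use days over the 12-week period, from 0 to 84, which "will be analyzed in a multivariate regression analysis, controlling for study group and treatment site interactions". The section on power considerations restates the model: "treatment effect will be investigated by means of a multivariate regression model with the total number of days of crack-cocaine use". It adds no covariate. The Protocol names baseline use as a covariate nowhere.

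The baseline value is collected. The assessments section lists among the baseline instruments "the Time Line Follow-Back (TLFB, pertaining to cocaine use in the previous month", and the same section and Table 1 repeat the TLFB at weeks 4, 8 and 12. The Protocol does not say outright that the 0-84 day total is built from these interviews, but no other daily record of use is described. The section on emergency unblinding also uses the patient's baseline value of the primary outcome to impute values after unblinding, so that value is meant to be available for analysis.

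The sample size rests on a difference that "is estimated to be 10 days, with a pooled standard deviation of 17 days", and concludes: "Given the two-sided alpha=0.10, and a 1-beta power of 0.80, n=36 patients are required in each study group". Randomisation is stratified by the four treatment centres and by nothing else.

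**The concern.** Under the study participants heading, anyone using cocaine on at least 8 days in the previous month is eligible, up to daily users, and all must have been dependent for at least 5 years. In such a group, recent use is the natural predictor of later use, and the trial measures it on the same scale. The Protocol names the site terms of its model but not this one.

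The point bears on the sponsor's own reasoning. The section on power considerations relaxes alpha to 0.10 to limit the loss of power in a small trial. A prespecified baseline covariate serves the same end without relaxing anything. Because stratification is by site alone, nothing in the design balances baseline use between the arms, and a model without it leaves any chance difference in the treatment contrast.

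**Working it through.** **Inputs from the Protocol.** Difference 10 days; pooled SD 17 days; two-sided alpha 0.10; power 0.80; 36 per arm, allocated 1:1.

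**Assumed input.** The correlation r between baseline TLFB days and the 84-day total. The documents do not give it, so a range is shown.

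**1. The Protocol's own figure.** n per arm = 2 × (1.645 + 0.842)² × 17² / 10² = 35.7, rounded up to 36. The standard error of the difference is 17 × √(2/36) = 4.01 days. Power with 36 per arm is 80.3% (normal approximation) or 79.6% (noncentral t, 70 df). The stated figure reproduces.

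**2. With baseline as a covariate.** The residual SD becomes 17 × √(1 − r²). Power uses the noncentral t with 69 df. The last column, 36 / (1 − r²), is the size per arm at which the unadjusted analysis would match the adjusted analysis of 36.

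| r (assumed) | Residual SD (days) | Power, 36 per arm | Gain over 79.6% (points) | Unadjusted n per arm to match |
|---|---|---|---|---|
| 0.2 | 16.66 | 81.0% | 1.4 | 37.5 |
| 0.3 | 16.22 | 82.8% | 3.2 | 39.6 |
| 0.5 | 14.72 | 88.7% | 9.1 | 48.0 |
| 0.7 | 12.14 | 96.5% | 16.9 | 70.6 |

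The normal approximation gives 81.7%, 83.4%, 89.2% and 96.8%. Spending further degrees of freedom on site and its interaction with group (63 df) changes the table by less than 0.1 point.

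**3. Chance imbalance.** If the arms differ at baseline by z standard errors, the unadjusted difference shifts by about r × 4.01 × z days, whatever the baseline SD.

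- A 2-standard-error imbalance shifts it by 0.5 × 4.01 × 2 = 4.0 days at r = 0.5, and by 0.7 × 4.01 × 2 = 5.6 days at r = 0.7.
- A shift of the full 10 days needs z = 10 / (r × 4.01), which is 8.3 at r = 0.3, 5.0 at r = 0.5 and 3.6 at r = 0.7.

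**The case against.** Four things can be said on the other side.

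*The text does not close the list.* It names control terms without saying that they are the only ones, and it reads as shorthand. A statistical analysis plan, not shown here, may add baseline. A reader might infer that the Protocol rules baseline out; it does not. What remains is that the Protocol chose to name terms and left this one out, so adding it later, without prior statement, would look like a departure from the plan.

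*The design meets its own target.* A reader might infer that the trial is underpowered for want of the covariate. It is not: 36 per arm gives about 80% power unadjusted, and the sample size takes no credit for adjustment. This stands in full.

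*The size of the gain is unknown.* A reader might call it substantial. That holds only if r is about 0.5 or more. Repeated measurement on one instrument in chronic users makes a moderate r plausible, but the entry floor of 8 days narrows the range, and one month has to predict 84 days. The site terms may also already absorb part of what baseline would explain. This stands as a limit on the claim.

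*Imbalance is not bias.* A reader might infer that chance imbalance in baseline use could by itself mimic or hide the 10-day effect. The third step of the working does not support that: it would take an imbalance of about 5 standard errors at r = 0.5, or 3.6 at r = 0.7. Ordinary imbalance is already covered by the SD of 17 and the nominal alpha. What survives is that adjustment removes its predictive part, which can be several days.

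A reader might also want to show a larger benefit under drop-out. The Protocol states no drop-out rate and plans multiple imputation for missing interview data, so no such figure is claimed here.

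**Conclusion.** The point holds as an improvement that costs nothing, not as an error. The primary model as written names no baseline use, the value is collected on the instrument used throughout follow-up, and prespecifying it would raise power from about 80% by between roughly 1 point (r = 0.2) and 17 points (r = 0.7).

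This rests on three assumptions:

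- r lies somewhere in that range;
- 17 days is the unadjusted SD, as the description of it as pooled suggests;
- the relation of total days to baseline days is close enough to linear for the residual SD formula to serve.

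If 17 days were already a residual SD after baseline adjustment, the gain would have been counted already and the 36 per arm would depend on the covariate being in the model. The recommendation would be the same.

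**What to change.** Before unblinding, add a sentence to the Protocol or the analysis plan: total days of use (0-84) will be regressed on treatment group, baseline TLFB days of cocaine use in the previous month, and site as the stratification factor; the adjusted mean difference will be reported with a 90% CI, matching the two-sided alpha of 0.10. Any group-by-site interaction should be examined secondarily, so that the primary result is a single treatment difference.

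The planned 72 patients, the assessments and the alpha stay as they are. The cost is the wording.

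### The primary model includes group-by-site interactions but defines no overall treatment contrast, although the trial is sized for one overall difference.

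*Protocol*

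**What the plan says.** The primary outcome (Protocol, Outcome Measures and Data Analysis) is the number of days of crack-cocaine use over 12 weeks, from 0 to 84. The same sentence gives the whole primary model: the outcome "will be analyzed in a multivariate regression analysis, controlling for study group and treatment site interactions".

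Power Considerations points back to that regression and then plans for one difference between the two study groups. The difference is put at 10 days, "with a pooled standard deviation of 17 days". The conclusion is: "Given the two-sided alpha=0.10, and a 1-beta power of 0.80, n=36 patients are required in each study group".

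Under General Study Design, allocation is 1:1 and "will be prestratified by treatment center (4 treatment centers"). The Protocol names the four sites but gives no planned enrolment per site. It does not say which coefficient or contrast is the primary test, how site is coded, or how the site effects are combined.

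**The concern.** A model with group, site and their interaction has eight parameters here (2 groups × 4 sites), and it allows a separate treatment effect at each site. It then contains no single treatment effect until someone says how the four are to be combined. If nobody does, the coding of the site variable decides:

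- Reference (indicator) coding: the group coefficient is the effect at the reference site alone.
- Sum-to-zero coding: it is the plain average of the four site effects, so a site with 8 patients counts as much as one with 40.

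The power section assumes neither in general. It assumes one comparison of 36 with 36. Two analysts who both followed the stated model could report tests of quite different power from the same data. The result is meant to help choose a medication for a confirmatory trial, and it should not hang on a coding choice. Since randomisation is stratified by centre, the adjustment that matches the design is a site main effect.

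**Working it through.** **Inputs from the Protocol:** difference 10 days, SD 17, two-sided alpha 0.10, power 0.80, 36 per group, 4 sites, 1:1 allocation.

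**Assumptions:** all 72 patients are analysed, allocation is 1:1 within each site, and the true effect is 10 days at every site. Patients per arm at each site are not given, so equal sites (9 per arm) and five unequal splits of 36 were tried.

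**1. The planned sample size.** n per group = 2 × [17 × (1.645 + 0.842) / 10]² = 35.74, rounded up to 36. Power at 36 per group is 80.3% (normal) or 79.6% (t test, 70 df). The stated figure reproduces, as a plain two-group comparison with no site or interaction term.

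**2. Group plus site main effects.** SE = 17 × √(2/36) = 4.01 days. Power from the noncentral t with 67 df is 79.5%, so 36 per group still fits.

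**3. Interaction kept, reference coding (72 − 8 = 64 df).** The coefficient uses one site only. With 9 per arm, SE = 17 × √(2/9) = 8.01 days, twice the planned SE, and power is 34%. Over the unequal splits, power runs from 21% (reference site with 4 per arm) to 58% (20 per arm).

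**4. Interaction kept, sum-to-zero coding (64 df).** With m_s patients per arm at site s, SE = 17 × √[2 × Σ(1/m_s) / 16].

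| Patients per arm by site (assumed) | SE (days) | Power |
|---|---|---|
| 9, 9, 9, 9 | 4.01 | 79.5% |
| 12, 12, 6, 6 | 4.25 | 75% |
| 14, 10, 7, 5 | 4.31 | 74% |
| 15, 11, 5, 5 | 4.49 | 71% |
| 18, 8, 6, 4 | 4.64 | 69% |
| 20, 8, 4, 4 | 4.94 | 64% |

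**5. Interaction kept, contrast weighted by site size (64 df).** Give each site effect the weight m_s/36. The variance is Σ(m_s/36)² × 2 × 17²/m_s = 2 × 17²/36, so SE = 4.01 days and power is 79.5% whatever the split. This is the planned comparison.

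**6. Simulation check.** In 4,000 simulated trials with four equal sites, power was 79.5% (group only), 79.3% (group + site), 33.8% (interaction, reference coding) and 79.3% (interaction, sum-to-zero coding).

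**The case against.** A reader might infer that the trial's primary test is a one-site comparison with 34% power, or that an interaction model cannot deliver the overall effect. The Protocol supports neither. It names no coding and no coefficient, and the power section describes the target as the difference between the two study groups. The 34% arises only if an analyst uses reference coding and then reports that coefficient as the trial result. Steps 4 and 5 show that the stated model can recover the planned comparison, at the cost of a few degrees of freedom. A reader might also infer that 36 per group is wrong; it is not.

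Four further points count against the concern:

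- The wording is loose. Study group is the exposure, not something to be controlled for, and the authors may have meant site adjustment plus a look at the interaction.
- Coding and contrasts are often left to a statistical analysis plan, which is not shown here.
- The unequal site sizes are assumed.
- This is a feasibility study with a lenient alpha. It is judged on acceptance, compliance, safety and satisfaction as well as efficacy, and alongside two parallel trials, so one coefficient does not decide alone.

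These points limit the size and certainty of the problem, but they do not remove it. The Protocol is not silent on the model: it writes the interaction into the primary analysis. An analysis plan would have to reinterpret that term, or add a contrast to it, before the analysis matched the power calculation.

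**Conclusion.** The point holds in a limited form. The stated primary model contains group-by-site interactions and no overall contrast, while the sample size rests on a single overall difference. For a true effect of 10 days with SD 17, power is about 34% if a one-site coefficient is read off with four equal sites. For the unweighted mean of site effects it is about 80% with equal sites and about 64% to 75% under the unequal splits tried. It is 79.5% for the size-weighted contrast or for the model with main effects only. All figures by site depend on assumed enrolment. The defect lies in the wording of the primary model, not in the number of patients.

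**What to change.** In Outcome Measures and Data Analysis, state the primary model as total days of use = study group + treatment site (main effect, the stratification factor) + baseline days of use. The treatment effect is then the group coefficient, reported with its 90% CI to match the two-sided alpha of 0.10. Describe group by site as an exploratory check of consistency between sites.

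Baseline days of use are already collected for the previous month by the Time Line Follow-Back. Including them is an improvement beyond the defect itself. The gain in precision cannot be computed here, because the Protocol gives no correlation between baseline and outcome.

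Alternatively, keep the interaction and pre-specify the contrast weighted by site size as the primary test.

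Either change costs one sentence, made before unblinding, and needs no further data or patients.
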